11. SAFETY ANALYSIS

11.1 ADVERSE EVENTS

The evaluation of adverse events (AE) will be monitored throughout the study, by direct observation at each visit.

All AE will be recorded (according to the definition), and not only those where the investigator suspects a causal relationship with the treatment. Adverse events of interest; i.e., those in which the investigator at each site must pay particular attention are those that have been defined as local safety (pain, irritation, itching and infection) and major maternal complications attributable to the pessary as chorioamnionitis, severe vaginal or cervical trauma.

All the AE will be encoded in MedDRA version 19.1 or higher to be summarized by System Organ Class (SOC) / Preferred Term (PT).

The following 3 overview tables will be generated by treatment group and overall:

1) Summary of the number and percentage of subjects with at least 1:

- AE
- Serious AE
- Non-serious AE
- Unexpected AE
- Severe AE
- Related AE
- Related serious AE
- AE leading to discontinuation from IMP

The percentage denominator will be the number of subjects in the safety analysis.

2) Summary presenting the number of AEs per subject categorized as 0, 1, 2, 3, 4, 5, and >5;

3) Summary of the number and percentage of AEs for:

- AEs
- Serious AEs
- Non-serious AEs
- Unexpected AEs
- Related AEs
- Related serious AEs
- AEs leading to discontinuation from IMP

The percentage denominator will be the total number of AEs.

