#### 5.5. Placement and repositioning of the cerclage pessary containing sustained-release progesterone

Once the cervix length and positioning have been examined by transvaginal ultrasound, and any vaginal infection has been ruled out or treated, the progesterone pessary should be implanted by a professional qualified and trained for that purpose. For placement, the participant must be lying in supine position.

The removal of the pessary will be done by vaginal examination at week 36 6/7 or earlier, if there is any medical indication for induction of premature labor or elective cesarean section. The pessary will also be removed from participants in preterm birth labor not responding to treatment with tocolytics.

During controls or visits to emergency departments or medical offices, participants who report vaginal discharge should be examined by a physician to rule out infection by relevant testing (vaginal discharge smears for PCR), and deliver the appropriate treatment without the need to remove the pessary. This condition will be considered an adverse event.

In the event that the medicated cerclage pessary is spontaneously expelled it, will be repositioned within maximum 72 hours; if this does not occur, the patient will be withdrawn from the study but considered in the final statistical analysis under the intention-to-treat principle.

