### Definition of Serious Adverse Event (SAE)

A SAE is any medical incidence that, at any dose:

- Results in death; or
- Is life-threatening (puts the subject, from the investigator's perspective, in an immediate risk of death due to the experience that took place. This includes direct life-threatening experiences but not those that could potentially put life at risk), or
- Requires or prolongs hospitalization of the patient (hospitalization is defined as an admission, regardless of length of stay, even if hospitalization is a precautionary measure in order to continuously monitor the patient). If this hospitalization is due to a non-worsening pre-existing condition, it is not to be considered as a serious adverse experience.

- Results in persistent or significant inability/disability (major impairment to the ability to perform daily life functions); or
- Is an abnormal congenital defect or birth defect
- Is considered a clinically significant medical event

A scheduled hospital admission, for example, for elective surgery, is not considered a SAE if documented at the time of enrollment.

All patients randomized in the study are pregnant women, therefore, hospitalizations related to scheduled parturitions/full term deliveries will not be considered as adverse events nor as serious or relevant adverse events.

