#### **Definition of Adverse Event of Special Interest**

Adverse events of special interest are adverse events considered important for assessment of the safety profile regardless of seriousness, expectancy, and severity classification.

Preterm birth is the birth of a fetus before 37 weeks of pregnancy. Preterm birth will be considered an event of special interest and should consequently be reported within 24 hours.

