9. TREATMENT COMPLIANCE

For Group A, at the start of each visit, it will be recorded the number of capsules dispensed at the previous visit and the number of capsules used, the treatment compliance will be estimated in percentage. The compliance should be between 80 and 120% for each patient.

For groups B and C, it will only be recorded if removal of the pessary was necessary. In this case the subject will be early terminated from the study and the reason for discontinuation will be recorded.

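### The SAP 11.1 overview rows, above all the serious-AE row, combine preterm birth and membrane rupture with other harms, so they can dilute, and under a large treatment effect reverse, an increase in other serious events

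*SAP*

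**What the plan says.** **Protocol 8, adverse event of special interest.** "Adverse events of special interest are adverse events considered important for assessment of the safety profile regardless of seriousness". The section then names one such event: "Preterm birth is the birth of a fetus before 37 weeks of pregnancy", and "Preterm birth will be considered an event of special interest and should consequently be reported within 24 hours".

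**Protocol 8, serious adverse event.** An event that requires or prolongs hospitalization is serious, and "hospitalization is defined as an admission, regardless of length of stay". The only exemption for deliveries is that "hospitalizations related to scheduled parturitions/full term deliveries will not be considered as adverse events nor as serious or relevant adverse events".

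**SAP 11.1.** The first overview table, by treatment group and overall, is a "Summary of the number and percentage of subjects with at least 1" AE, serious AE, severe AE, related AE, related serious AE, or AE leading to discontinuation of the product, among other rows. No row or second version sets preterm birth apart. The SAP's list of events of interest covers local symptoms, infection and major maternal complications attributed to the pessary. Preterm birth is not on it.

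**SAP 10, secondary analysis.** Premature rupture of membranes, a secondary efficacy outcome, is identified from the adverse-event records.

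**Removal of the pessary.** Protocol 5.5: "The pessary will also be removed from participants in preterm birth labor not responding to treatment with tocolytics". SAP 9, on a woman whose pessary has to be removed: "In this case the subject will be early terminated from the study and the reason for discontinuation will be recorded".

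**Other safety output.** SAP 11.2 counts women per arm by system organ class and preferred term for AEs, serious AEs, related AEs and serious related AEs. Protocol 9.2 compares the proportion of women with adverse events between doses by Fisher's exact or chi-square test.

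**The concern.** Local and systemic safety of the pessary is a stated objective in both documents. A reader of the overview table will take the serious-AE row as a summary of harm. If preterm deliveries are in that row, part of it measures whether the treatment works. A pessary that lowers preterm birth would pull its own serious-AE percentage down, and this could offset a rise in other serious events. A pessary that fails would show a higher percentage with no other harm. The any-AE comparison in Protocol 9.2 has the same mixture. Because SAP 11.1 omits preterm birth from its events of interest, nothing in the SAP tells the programmer to show it separately.

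**Working it through.** **1. Classification.** Take an unscheduled spontaneous delivery in hospital at 33 weeks.
- It is a birth before 37 weeks, so it is an event of special interest, which Protocol 8 defines as an adverse event.
- It involves an admission and is neither scheduled nor full term, so the delivery exemption does not cover it. On a plain reading it is serious. No sentence says so outright.
- In SAP 11.1 this woman counts once in the AE row and once in the serious-AE row. So does a woman with severe cervical trauma and a term birth. The row cannot tell them apart.

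**2. Inputs.** The documents state no AE or SAE rate, so there is no plan figure to reproduce and all rates here are assumptions.
- Preterm birth in the capsule arm, p: 10% to 40%. Protocol 2 gives 7% to 10% of births in general, and a predictive value of 40% for birth before 35 weeks in higher-risk women with a short cervix found at 18-22 weeks.
- Relative reduction with the pessary: 40%, 20% or none.
- Other serious events: 5% with capsules, 10% with the pessary, independent of preterm birth.

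**3. Formula.** Women with any SAE = 1 − (1 − preterm rate)(1 − other-SAE rate). Example at p = 20% with a 40% reduction: capsule 1 − 0.80 × 0.95 = 24.0%; pessary 1 − 0.88 × 0.90 = 20.8%.

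| p, capsule | Capsule, any SAE | Pessary, 40% fewer | Pessary, 20% fewer | Pessary, no effect |
|---|---|---|---|---|
| 10% | 14.5% | 15.4% | 17.2% | 19.0% |
| 15% | 19.3% | 18.1% | 20.8% | 23.5% |
| 20% | 24.0% | 20.8% | 24.4% | 28.0% |
| 30% | 33.5% | 26.2% | 31.6% | 37.0% |
| 40% | 43.0% | 31.6% | 38.8% | 46.0% |

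The true difference in other serious events is +5 points in every cell. With no effect on preterm birth it shrinks to between +4.5 and +3.0 points and never reverses.

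**4. Where the sign changes.** Equal rows require 0.95(1 − p) = 0.90(1 − kp), where k is the pessary's preterm rate relative to capsules.
- 40% reduction (k = 0.6): p = 0.05 / (0.95 − 0.54) = 12.2%.
- 20% reduction (k = 0.8): p = 0.05 / (0.95 − 0.72) = 21.7%.

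Below these values there is dilution; above them, reversal.

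**5. A second set of rates.** With other serious events at 2% v 8% and a 40% reduction, the row reads 11.8% v 13.5% at p = 10%, 21.6% v 19.0% at 20%, and 31.4% v 24.6% at 30%. The pattern is the same.

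**6. The any-AE row.** Discharge, pain, irritation and infection are also AEs. Assume other AEs in 50% v 70% of women and a 40% reduction in preterm birth. The row is then 60.0% v 73.6% at p = 20% and 65.0% v 75.4% at p = 30%. The excess stays visible (+13.6 and +10.4 points against a true +20). Preterm birth is the only AE in 17% to 23% of capsule women with an AE, and in 5% to 7% of pessary women with one.

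**7. What the preferred-term tables add.** They give women per arm for each term, so chorioamnionitis or trauma has its own line. A woman can appear under several terms, so the lines cannot be added. The number of women with any serious event other than preterm labour, preterm delivery or membrane rupture lies somewhere between the largest remaining line and the sum of those lines, and no planned table states it.

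**The case against.** The strongest reply is that the planned output already shows specific harms. SAP 11.2 counts women, not only events, by preferred term for serious and serious related AEs. SAP 11.1 itself has rows for related and related serious AEs, which bear more directly on the device. No test of SAE totals is planned. This stands, and it limits the problem to the overview rows and the any-AE comparison in Protocol 9.2. It does not supply the missing count, and relatedness is judged by investigators who know the treatment.

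A second reply is that seriousness is inferred. Events of special interest count regardless of seriousness, and a separate 24-hour rule for preterm birth would be largely redundant if every case were already serious. Protocol 8 also defines an adverse experience as unexpected, and the delivery exemption is unclear for an indicated preterm delivery. This stands too, but sites could then code the same event differently, which is a reason for the SAP to state a rule.

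A third reply concerns the discontinuation row. Protocol 5.4.5 closes a case at preterm birth, and the SAP 6 per-protocol set treats the end of pregnancy as completion. Removal of the pessary in refractory labour may therefore never be coded as an AE leading to discontinuation. That row is only possibly affected.

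A reader might infer more: that the AE and SAE totals largely re-count the efficacy outcome and will conceal a device harm. The documents do not support this. They give no event rates. Step 6 shows that the any-AE row need not be dominated by preterm birth. The special-interest event (any birth before 37 weeks) is wider than the primary outcome, which is spontaneous delivery judged at weeks 32 and 34. Reversal also requires a clear advantage over an active control: Protocol 2 credits prophylactic progesterone with about 40-45% less spontaneous preterm birth, and capsule women receive progesterone.

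**Conclusion.** The point holds as a defect of presentation. As written, the overview serious-AE row mixes preterm birth and membrane rupture with other serious events, and SAP 11.1 disagrees with Protocol 8 on which events are of special interest. Under the assumed rates a doubling of other serious events from 5% to 10% is diluted to +0.9 points at 10% preterm birth with a 40% reduction, and becomes −3.2 points at 20%. With a 20% reduction it is diluted to +0.4 points at 20%, and the sign changes only above about 22%. With no reduction there is dilution only.

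These sizes rest on assumed rates, on independence, and on reading unscheduled preterm admissions as serious. Individual harms remain visible in the preferred-term tables. The change is a cheap improvement and not a condition for a valid safety analysis.

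**What to change.** In SAP 11.1:
- State whether preterm birth and its admission are counted as an AE and as serious, and reconcile the list of events of interest with Protocol 8.
- Give preterm birth its own by-arm row.
- Pre-specify a list of preferred terms: preterm labour, preterm delivery, premature rupture of membranes.
- Show the rows for any AE, serious AE, related AE, related serious AE and AE leading to discontinuation of the product side by side, with and without these terms.

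Do the same for the comparison of AE proportions in Protocol 9.2. Make neither version the sole main comparison, because the device could itself cause labour or membrane rupture, and a headline without these terms would hide that. The 24-hour reporting of preterm birth is unaffected.

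Cost: SAP wording, one term list and a few more table rows. No new data or patients are needed.

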11.2 INCIDENCE RATES AND NUMBER OF EVENTS

The incidence of an AE is defined as the number of subjects with occurrence of this AE during the period of interest. The incidence rate (CIR for crude incidence rate) of an AE is defined as the number of subjects with occurrence of this AE during the period of interest divided by the total number of subjects in the respective group (e.g., dose group).

The incidence, incidence rate, the number of events and the percentage of events (related to the total number of events) will be summarized by PT (sorted by decreasing incidence rate in the overall column) for

- AEs
- related AEs
- AEs leading to treatment discontinuation

A separate table per type of AE will be prepared. Only AEs occurring in at least 5% of subjects overall will be included in the text. Tables will be sorted by decreasing incidence overall.

The incidence, incidence rate, the number of events and the percentage of events (related to the total number of events) will be summarized by SOC and PT (sorted alphabetically) for each

- AEs
- serious AEs
- non-serious AEs
- related AEs
- serious treatment related AEs
- AEs leading to treatment discontinuation

For serious AEs, the incidence, incidence rate, the number of events, and the percentage of events will also be presented for serious treatment related AEs, serious fatal AEs and serious fatal related AEs.

For all enrolled subjects, the incidence, incidence rate, the number of events, and the percentage of events (related to the total number of events) will be summarized by SOC and PT (sorted alphabetically) for each.

The number and percentage of events will be summarized by SOC and PT (sorted alphabetically) for the following AE descriptors. Presentation will be for AEs only.

- intensity: mild, moderate, severe
- causal relationship to the imp: related (with subcategories: possible, probable/likely, certain), not related (with subcategories: not related, unlikely), unknown (with subcategories: conditional/unclassified, unassessable/unclassifiable, causal relationship missing)
- outcome: recovered/resolved, recovering/resolving, not recovered/not resolved, recovered/resolved with sequelae, fatal, unknown
- non-IMP related countermeasures: none, newly started medication, others
- action taken with imp: dose not changed, dose reduced, drug interrupted, trial discontinuation, unknown.

Denominator for percentage calculation will be the number of all AEs for the presentation overall SOC, and the number of AEs per SOC or PT respectively, for the presentation per SOC or PT, respectively.

The following tables will be presented as part of this analysis:

- Table of AE that ended in discontinuation, presented by SOC and PT
- Table of AE presented PT
- Table of serious AE presented PT
- Table of non-serious AE presented PT
- Table of related AE presented PT
- Table of AE related and serious, presented PT
- Table of AE presented SOC and PT
- Table of serious AE presented SOC and PT
- Table of non-serious AE presented SOC and PT
- Table of related AE related, presented SOC and PT
- Table of related and serious AE presented PT
- Table of AE presented SOC and PT and intensity
- Table of AE presented SOC and PT and action taken
- Table of Unexpected AE (non-serious and serious) presented PT
- AEs by primary SOC, PT, and outcome
- AEs by primary SOC, PT and non-IMP related countermeasure
- AES by primary SOC, PT, and causal relationship to IMP

11.3 PREVIOUS AND CONCOMITANT MEDICATIONS

Incidence rates for previous and concomitant medications will be summarized by number of subjects with at least one medication, the naming convention will be codified by Anatomical Therapeutic Classification (ATC) / Therapeutic Chemical Level II.

12. TABLES, LISTINGS AND FIGURES

All the tables, listings and figures will have a complete description of the content, including the name of the company, protocol, population studied and date of elaboration. On the footnote will be indicated the database, program name and output name. All figures will make reference to the tables and listings utilized for their elaboration. All the lists will be ordered by subject number.

Data listings for all data sets will be displayed as an annex to the CSR. Also the following version of the listings will be included:

- Subject completion/discontinuation – all enrolled subjects
- Adverse events leading to trial discontinuation – all enrolled subjects
- Other reasons for discontinuation – all allocated subjects
- Serious adverse events other than death– all enrolled subjects
- Adverse events leading to IMP dose decrease or interruption of IMP – all enrolled subjects
- Adverse events – all enrolled subjects
- Laboratory and vital signs parameters

